5.4 Subject number

Prior to any study procedures being conducted, the subject must sign the informed consent form. Each subject who has signed the informed consent form will be assigned a screening number. Upon randomization, each subject will be assigned a subject number that will be allocated in ascending order within each center. A screen failure is a subject who signed the informed consent but never enrolled (i.e. was randomized and/or received treatment) in the study. For screen failures, the subject source documents should indicate which assessments have been made and the reason why the subject was determined to be a screen failure. A screen failure should not be re-entered in the study. A subject is considered enrolled when they have signed the Informed Consent Form (ICF) and are randomized and/or treated.

For the duration of the clinical study, each subject will be identified using the subject number for all documentation and discussion. A subject identification log is required to be kept in the Investigator file.

5.5 Withdrawal of subjects

An investigator may decide to discontinue a subject from the clinical study for safety reasons.

Although the importance of completing the entire clinical study should be explained to the subject by the clinical study personnel, any subject is free to discontinue participation in this clinical study at any time and for whatever reason, specified or unspecified, and without any prejudice. No constraints are to be imposed on the subject, and when appropriate, a subject may be treated with other conventional therapy when clinically indicated.

When a subject does not complete the clinical study, he/she will be fully assessed, if such assessment is possible. The procedures designated for the Early Termination (ET) visit should be completed for all subjects discontinuing the clinical study and the appropriate eCRF should be completed.

All discontinuations and the reason for discontinuation are to be documented by the investigator on the Exit form.

For discontinuation due to and AE, the Adverse Event form is to be completed. The investigator should also ensure that the subject receives suitable therapy for the AE.

A subject who has been randomized cannot be replaced by another subject if he/she discontinues the clinical study for any reason.

	Title 43USTT1904 CSP Infraorbital Hollows	Doc id MA-40833
--	---	---------------------------

Pregnancies occurring during the screening period are considered as screening failures; they should be recorded as such in the eCRF and no pregnancy form is to be completed.

In case of a pregnancy occurring after the baseline visit, follow the procedures described in section 8.5.12. The subject may remain in the study, but no invasive procedure should be conducted.

The Sponsor may also decide to prematurely terminate or suspend a subject's participation in the clinical study.

Potential reasons for discontinuation are defined below:

The withdrawal criteria are:

- **Medical Reasons** If the subject suffers from a medical condition and/or Adverse Events that, in the judgment of the Investigator makes it medically necessary to withdraw the subject. The specific rationale for Investigator-initiated withdrawal of a subject for medical reasons should document the specific condition for withdrawing the subject.
- **Withdrawal by Subject:** Includes consent withdrawal, subject relocation, schedule conflicts. A subject can withdraw their consent to participate in the study at their own request or be withdrawn from participation in the study at the request of their legally authorized representative at any time for any reason.
- **Lost to follow-up:** If a subject does not return for a scheduled visit, reasonable effort shall be made to contact that subject, confirm with three documented phone calls and a certified letter (delivery receipt requested) without answer before declaring the subject lost to follow-up.
- **Other:** This category is to be used for a subject who discontinues due to a reason other than as specified in the pre-defined categories above. Explain the reason for discontinuation.

If reason for discontinuation is “withdrawal by subject” or “other”, the subject will be questioned to rule out the possibility of an AE. If the AE led to discontinuation then “Adverse Event” should be chosen as the reason for discontinuation, rather than “withdrawal by subject” or “other”.

If an AE which, according to the Investigator's assessment, is related to the use of any of the study products and is still ongoing at the time of the withdrawal, the Investigator shall follow-up the subject until the AE resolves, is assessed by the Investigator to be “chronic” or “stable” or subject is lost to follow up. Follow-up information shall be reported on the AE follow-up form.

6. Study Products

The term “study products” refers to *Restylane-L*. The study product will be provided by the Sponsor.

 <small>EST. 1981</small>	<small>Title</small> 43USTT1904 CSP Infraorbital Hollows	<small>Doc id</small> MA-40833
--	--	--

Effective date: 2021-12-15 20:29

6.1 Investigational product

The investigational device (i.e. study product) is *Restylane-L* injectable gel. The sterilized gel contains 20mg/mL stabilized HA and 3 mg/mL lidocaine hydrochloride in a physiological buffer. Each syringe contains 0.5 mL gel.

Restylane-L is supplied sterile, 0.5 mL filled in a disposable glass syringe with a luer lock fitting. *Restylane-L* is co-packed with one sterilized Thin Wall (TW) needle as indicated on the carton (29 G x 1/2").

6.2 Additional products and materials

The sponsor will provide Urine Pregnancy Tests, cotton wisps, and monofilaments to each study site.

Topical or local anaesthesia may be used at the discretion of the treating Investigator before the treatment. If used, the anaesthesia shall be supplied by the study site. Type of anaesthesia, administration route, product name, and quantity used must be recorded in the eCRF.

Small blunt tip commercially available cannulas TSK Steriglide 25G x 1 1/2" and TSK Steriglide 27G x 1 1/2" will be supplied by the study sites (for sites using cannula). The co-packed needle should be used as incision needle with each cannula.

6.3 Labelling and storage

Labelling will be performed according to United States Code of Federal Regulations (CFR) 21 CFR 812.5: Labelling of investigational devices. The carton will be labeled with the lot number as well as expiration date and the CTN and the following:

"CAUTION - Investigational Device. Limited by US Law to Investigational Use."

The syringes should be stored in their original packaging at a temperature up to 25°C (77°F), protected from sunlight and freezing. Opened packages or partially used devices should not be reused. Detailed product information is provided in the IFU.

6.4 Product accountability

The study products will be released to the Investigator or his/her authorized designee after study approvals have been received from the FDA and IRB and the CTA has been signed by all parties.

The Investigator must ensure that the study products are kept in a secure location, with access limited to those authorized by the Investigator.

The study products must be traceable from the manufacturer to their use in subjects until return or disposal. It is therefore important that the Investigator maintain accurate product accountability records, i.e. documentation of the physical location of all study products, deliveries, and return of study products between the Sponsor and the Investigator, and documentation of administration of product to the subject.

When the study is completed, all unused or expired study product at each study site should be returned to the Sponsor representative for destruction, or be destroyed locally at the site if documented as agreed with Sponsor.

Any malfunctioning study products should be reported as described in section 8.6.

	Title 43USTT1904 CSP Infraorbital Hollows	Doc id MA-40833
--	---	---------------------------

Products deliberately or accidentally destroyed during shipment or at a study site should be accounted for and documented. Used syringes, needles, and any unused material must be discarded immediately after the treatment session and must not be reused due to risk for contamination of the unused material and the associated risks including infections according to standard procedures at the site. Disposal of hazardous material, i.e. syringes and needles must conform to applicable laws and regulations. The study products must not be used outside the study.

6.5 Treatment

The investigational product is reserved for use by Treating Investigators who are experienced in infraorbital injection procedures. Before treatment the subject will be informed about the expected post-treatment events that should be recorded in the Subject Diary and potential risks involved with the treatment and when to contact the Investigator in case of emerging symptoms. The investigator must be trained on, and have at hand, the relevant clinical practice guidelines¹ and the actions to be taken if visual disturbances occur. The investigator should also have reviewed the Intravascular Treatment Protocol supportive tool provided separately in the Investigator file.

6.5.1 Pre-Treatment procedure

A visual function assessment should be performed prior to injection of the investigational product, see section 8.2.

The study product contains lidocaine hydrochloride, but additional topical or local anesthesia or ice pack may be used at the discretion of the Treating Investigator to enhance the experience of the subject. Any additional topical or local anesthesia used should be recorded in the source documentation and on the eCRFs

6.5.2 Treatment Regimen (dose and interval)

Detailed information regarding the injection procedure, pre- and post-treatment care and patients instructions are provided in the IFU.

Restylane-L is to be placed in the supraperiosteal plane. The infraorbital treatment area is at the junction of the lower eyelid and midface where a volume deficit has formed. This area is bordered by the nasal sidewall medially, the temporal region of the bony orbit laterally, the bulk of the lower eyelid superiorly, and the superior aspect of the mid-face inferiorly.

The injection technique is at the discretion of the Investigator. For needle serial puncture is recommended and for cannula fanning technique is recommended. The injection should be performed with a constant low-to-moderate pressure on the plunger. Slight elevation of the skin should be observed without significant blanching of the skin. To avoid visible lumps and/or discoloration, avoid injection of *Restylane-L* superficially. When the injection is complete, the treated area may be gently massaged, if necessary.

¹ Alam M, Gladstone H, Kramer EM, et al. ASDS guidelines of care: injectable fillers. *Dermatol Surg.* 2008; 34 (suppl 1): S115-S148.

	Title 43USTT1904 CSP Infraorbital Hollows	Doc id MA-40833
--	---	---------------------------

Allowed maximum injection volume for initial injection, touch-up and end of study treatment is 1,0 mL per side at each treatment session. Slow injection is recommended and overcorrection should be avoided.

For the optional treatment at 12 months sites will continue to use needle or cannula for injection based on the initial selection for each particular site.

6.5.3 Post-treatment care

Post treatment procedures with ice pack or gentle massage are allowed as per investigator normal procedure. Ice pack can be applied for a short period if the treated area is swollen. Gentle massage can be applied for any irregularities.

After the injection, some common injection-related reactions might occur. These reactions include erythema, swelling, pain, itching, bruising or tenderness at the implant site. Typically, resolution is spontaneous within one week after injection into the skin.

Post-injection Vision Function Assessment tests including the Snellen visual acuity test, Extraocular muscle function test and Confrontation visual field, by the treating investigator will be repeated 30 minutes after injection, see section 8.2.

Acetaminophen may be taken if instructed by the physician. Any medication or therapy used by the subject must be recorded in the CRF.

The subject must avoid exposing the treated area to heat (sun bathing, sauna, steam baths, etc.) or extreme cold until any signs of initial swelling and redness have disappeared.

6.5.4 Post-trial provisions

In time, the implant will be degraded in the body and additional treatments will be necessary to maintain the aesthetic result. Subjects will be offered optional treatment at the 12 months follow-up visit. The same procedure as described in section 6.5.1 and 6.5.2 should be followed. After the final study visit, the Sponsor will not supply any more treatments to the subjects, even if the result does not persist.

6.5.5 Treatment compliance

Not applicable; the treatment will be administered by the injector at the investigational site.

7. Effectiveness Assessments

7.1 General information

The methods for collecting efficacy data are described in the following sections. To minimize inter-observer variability, every effort should be made to ensure that preferably the same individual who made the initial baseline determinations completes all corresponding follow-up evaluations.

7.2 Galderma Infraorbital Hollows Scale (GIHS)

The GIHS is a 4 point scale for assessment of Infraorbital Hollows (Appendix 2). Each score in the GIHS is exemplified by Photographic images of the scale. The blinded evaluator and treating investigator will perform live assessment of the subject's left and right Infraorbital Hollow separately.

	Title 43USTT1904 CSP Infraorbital Hollows	Doc id MA-40833
--	---	---------------------------

The blinded evaluator will perform GIHS assessments at:

- screening and baseline
- 3, 6, 9 and 12 months after randomization
- 3 and 6 months after optional treatment. The evaluator is considered unblinded as these assessments are performed for all subjects receiving the optional treatment.

The treating investigator will perform GIHS assessment at:

- screening and baseline
- 1 and 12 months after randomization

7.3 Global Aesthetic Improvement Scale (GAIS)

The 7-graded GAIS will be used to live assess the aesthetic improvement of the Infraorbital Hollows by the Treating Investigator and the subject, by comparing to a photograph taken at the baseline visit before the first treatment. The Treating Investigator and the subject will, independently of each other, respond to the question: “How would you describe the aesthetic improvement of your tear troughs today compared to the photograph taken before treatment?” by using the respective categorical scale below.

GAIS will be assessed at 1, 3, 6, 9 and 12 months after randomization, at 1 month after optional touch-up and at 1, 3, and 6 months after optional treatment.

Table 3: Global Aesthetic Improvement Scale (GAIS)

[figure not shown]
Rating (Treating Investigator and Subject)	Definition (only for Treating Investigator)
Very Much Improved	Optimal aesthetic result for the implant for this subject.
Much Improved	Marked improvement in appearance from the initial condition, but not completely optimal for this subject.
Improved	The appearance is improved from the initial condition.
No Change	The appearance is essentially the same as baseline.
Worse	The appearance is worse than the initial condition.
Much Worse	Marked worsening in appearance from the initial condition.
Very Much Worse	Obvious worsening in appearance from the initial condition.

The Treating Investigator and Subject shall independently rate their assessment for aesthetic change comparing the appearance at follow-up visits to baseline photographs (obtained prior to injection at baseline

GALDERMA <small>EST. 1981</small>	<small>Title</small> 43USTT1904 CSP Infraorbital Hollows	<small>Doc id</small> MA-40833
---	--	--

Effective date: 2021-12-15 20:29

CCI

[figure not shown]

7.7 Photography

Photographs will be taken prior to treatments with study product and at every follow-up visit in order to document treatment effect. Photographs may also be taken to document AEs at the Treating Investigator's discretion. Baseline photographs may be used as a reference in the GAIS assessment by the Treating Investigator and subject. Site personnel will be thoroughly trained in the photographic equipment and techniques before study start.

Camera equipment will be provided by the Sponsor or their designee and standardized photographs should be achieved. Further details regarding photography procedure will be specified in a separate user guide.

CCI

8. Safety Assessments

8.1 Assessment of AEs by direct question to subject and evaluation of subject

Safety evaluations for this study include an interview of the subjects at each visit to obtain information about any medical occurrence that meets the definition of an AE. Each subject should be questioned about AEs at each study visit following the screening visit. The question should be asked: "Since your last clinical visit have you had any health problems?" Information on AEs can also be obtained from signs and symptoms detected during each examination by the Investigator or designee, which should include visual inspection of the treatment area.

AEs must be documented in the source document and eCRF without regard for cause or relation to investigational product. If in the process of the interview, additional information regarding

Effective

Version: 10.0

	Title 43USTT1904 CSP Infraorbital Hollows	Doc id MA-40833
--	---	---------------------------

medical history or pre-planned medical or surgical procedures is revealed, it must be documented in the source document(s) and eCRF.

It is the responsibility of the Investigator to determine severity of the AE and relatedness of the event to the study product.

8.1.1 Adverse Events of special interest

All incidences of visual disturbances, regardless of relationship to study product or seriousness, are considered Adverse Events of Special Interest (AESIs) and include but are not limited to the following: any change in vision, any loss of vision, blurry vision, double vision, pain in or around the eye, blind spot or shadow in the visual field, trouble moving eyes, any change in Snellen visual acuity including change of one line or greater.

AESIs should be reported (using the Adverse Event Clarification Form) within 24 hours of awareness to the Sponsor (following the instructions in section 8.5.6) via email to [contact]. Appropriate follow up should be conducted in order to determine the cause, severity, seriousness, outcome, and relationship to the study product or procedures.

8.2 **Vision function assessment**

Vision function assessments will be performed both prior to and 30 minutes post injection of the study product at baseline and optional touch-up and optional treatment. These assessments include Snellen visual acuity, extraocular muscle function, and confrontation visual field testing.

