8.2.1 Snellen visual acuity test

A Snellen Eye Chart will be used to assess visual acuity for distance vision. Visual Acuity will be conducted using the subject's best distance correction (e.g. contacts or eye glasses) at a distance of approximately 6 feet from the chart. Each eye will be measured separately by either using an occluder or having the subject cover each eye. The subject will be asked to start reading the letters at the top of the chart working their way to the bottom. The smallest row of letters that the subject can read will indicate their visual acuity listed on the chart. Snellen Visual Acuity will be recorded in their source documentation and eCRF. If there is one or more visual acuity line changes during the course of study, these should be reported to the Sponsor within 24 hours of awareness as an AESI. These events should be reviewed and assessed by the Investigator as an Adverse Event.

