8.3 Subject Diary Data

The subject shall evaluate local tolerability in a 28 days diary, starting on the day of each treatment. The presence and maximum intensity of pre-defined, expected post-treatment events, i.e. bruising, redness, pain, tenderness, lumps/bumps, itching and swelling shall be assessed for the treated area. The Subject Diary will also have an area for the subject to report any other symptoms outside the pre-identified. Especially symptoms like change in vision change in skin color or crusty/scabby skin around the eyelids, dizziness, confusion, weakness or numbness in arms or legs, changes to consciousness or alertness, difficulty speaking/speech impairment, face droop, headache and fever should be recorded. The diary will also include instructions for the subject to:

- Contact an eye doctor (retinal specialist or ophthalmologist) if they experience change in vision (i.e. vision loss, blurriness, double vision, pain in or around eye, blindness, blind spots, problems moving your eyes), change in skin color or crusty/scabby skin around the eyelids
- Call 911 and seek immediate medical attention if signs of stroke or subject experience dizziness, confusion, weakness or numbness in face, arms or legs, changes to consciousness or alertness, difficulty speaking/speech impairment, face droop

The Investigator or study staff should review the diary for completion and clarify any events as needed. For events that are ongoing at the time of diary completion, the Investigator should follow them and record resolution in the subject's study file and eCRF. Diary data will be analyzed and displayed separately from AE data.

CCI

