#### Adverse Events of Special Interest (AESI)

2022-08-17 17:26

Due to the injection location of this study, AESIs will be considered and collected. All incidences of visual disturbances, regardless of relationship to study product or seriousness, will be considered as a potential AESI. These include, but are not limited to, the following: Any change in vision, any loss of vision, blurry vision, double vision, pain in or around the eye, blind spot or shadow in the visual field, trouble moving eyes, any change in Snellen visual acuity including change of one line or greater.

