#### 2.5.4 Vision Function Assessment

[figure not shown]
For the extraocular muscle function test and confrontation visual field vision function assessments (specified in Section 1.5.2) the number and percentage of subjects reporting normal and abnormal test results will be presented by treatment group and by visit.

For Snellen visual acuity test, subjects that experience a worsening of 1+ line change in at least one eye during the course of the study will be summarized by eye, treatment group, and visit. Only subjects that experience a worsening line change will be considered in the analysis; the number and percentage of subjects that experience a worsening of 1+ line change in at least one eye during the course of the study will be presented. The number of subjects with a non-missing Snellen assessment at a respective visit will be used as the denominator.

A 1+ worsening line change in Snellen visual acuity is when a subject moves up at least one line of letters on the Snellen Eye Chart (Figure 1). For example, if a subject's visual acuity at baseline is 20/40 for the left and right eyes and then at Visit 3 is 20/70 for the left eye and 20/50 in the right eye, the subject experienced a 2-line worsening for the left eye and a 1-line worsening in the right eye.

Figure 1. Snellen Eye Chart

2022-08-17 17:26

The visual function assessment data will also be presented by treatment and subject in data listing. This listing will only include subjects with a change in visual function as determined by any of the three vision assessments.

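### The AESI rule gives no direction for a Snellen line change and does not separate eye-area pain from expected diary pain, so the single Any AESI row can mix non-harm with visual harm

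*Protocol*

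**What the plan says.** **AESI definition.** Protocol 8.1.1 makes AESIs of "All incidences of visual disturbances, regardless of relationship to study product or seriousness". Its examples include "pain in or around the eye, blind spot or shadow in the visual field, trouble moving eyes" and "any change in Snellen visual acuity including change of one line or greater". Loss of vision is a separate item in the same list.

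**Snellen rule.** Protocol 8.2.1 says: "If there is one or more visual acuity line changes during the course of study, these should be reported to the Sponsor within 24 hours". The report is made as an AESI, and the Investigator is to review and assess the change as an adverse event.

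**SAP definition.** SAP 1.5.1 repeats the list, including "pain in or around the eye, blind spot or shadow in the visual field". It calls these events potential AESIs and gives no step that turns a potential AESI into a counted one.

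**SAP outputs.** The adverse-event overview in SAP 2.5.2 has two AESI rows, Any AESI and Any Serious AESI, with no split by component. For the Snellen table, SAP 2.5.4 states: "Only subjects that experience a worsening line change will be considered in the analysis".

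**Diary.** Protocol 8.3 says the "expected post-treatment events, i.e. bruising, redness, pain, tenderness, lumps/bumps, itching and swelling shall be assessed for the treated area". Diary data are displayed separately from adverse-event data.

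**The concern.** Acuity has a good and a bad direction. The AESI rule ignores it, while the SAP's own Snellen table respects it. A subject who reads one line further down the chart at the 30-minute repeat meets the literal AESI wording but is absent from the Snellen table.

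Pain raises a second question. The treated area lies along the lower eyelid and orbital rim, so ordinary pain in it is also pain around the eye. One section makes that an expected diary symptom and another an AESI, and sites may resolve this differently.

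At stake is what a reader can take from the Any AESI row. It may combine loss of vision, retest gains and injection-site pain in one number, and its content may vary by site. A comparison with the untreated arm is further affected because scheduled retesting differs between the arms.

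**Working it through.** The documents give no AESI rate, no Snellen retest variability and no safety precision target, so there is no plan figure to reproduce. The check compares the texts and then illustrates the possible size.

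**1. Direction.**
- Protocol 8.1.1 and 8.2.1: any change, threshold one line, no direction.
- Protocol 8.2.2 and 8.2.3: changes in eye movement or visual field are assessed for a potential adverse event. The Snellen rule in 8.2.1 is firmer: line changes are reported as AESIs and assessed as adverse events.
- Protocol 8.5.1: an adverse event must be untoward, which points against counting a gain.
- SAP 2.5.4: worsening of at least one line only.

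These texts do not settle whether a gain is counted.

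**2. Can the components be recovered from the tables?** Not directly. The Snellen table uses as denominator the subjects with a non-missing test at the visit. Adverse-event percentages generally use the Safety population. One counts test results and the other reported events, so subtraction does not isolate the gains.

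**3. Who is tested.** In the schedule of events, the day-1 and month-1 vision tests apply to subjects randomized to treatment (footnote 9). The day-14 visits exist only after an injection (footnote 4). Before month 12, an untreated subject therefore has no scheduled post-baseline Snellen test.

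**4. Illustration of size.** Inputs:
- Tests after initial treatment: 30 minutes and day 14, two eyes, so m = 2 × 2 = 4 eye-tests (schedule of events).
- Treated subjects: about 282 (Protocol 10.11, SAP 2.7).
- p = chance that one eye-test reads a line better through retest noise: 2-5%. This is an assumption; the documents give no value.

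The chance that a subject has at least one such reading is 1 − (1 − p)^m if tests are independent. It is p if tests are fully correlated within a subject.

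| p | Independent | Of 282 | Fully correlated | Of 282 |
|---|---|---|---|---|
| 2% | 1 − 0.98^4 = 7.8% | 22 | 2% | 6 |
| 5% | 1 − 0.95^4 = 18.5% | 52 | 5% | 14 |

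The range is therefore about 2-19% of treated subjects, or 6 to 52 people. If 2-5% is instead the rate of change in either direction and half are gains, p is 1-2.5%. Independence then gives 1 − 0.99^4 = 3.9% (11) to 1 − 0.975^4 = 9.6% (27).

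A touch-up adds tests before injection, 30 minutes after and at day 14, so m = 10. For a subject who has one, independence gives 1 − 0.98^10 = 18.3% to 1 − 0.95^10 = 40.1%.

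These are chances of a gain being read, not of its being counted. Investigator review may remove some, and some of these subjects would be in the row for another reason.

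**5. Pain.** Protocol 8.3 lists pain in the treated area as an expected event. In its instructions to subjects, the same section lists pain in or around the eye under change in vision. Protocol 8.5.4 says expected events are assessed separately, but also names subject diaries as a source of adverse events. No section says when treated-area pain becomes an AESI. The documents give nothing from which to size this overlap.

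**The case against.** The strongest reply is that the row is deliberately inclusive and that other outputs already separate its parts.

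- The list is framed as visual disturbances, an adverse event must be untoward, and the Investigator assesses each line change. A gain may never be recorded. This stands as a reason not to say that gains *are* counted. It does not remove the ambiguity, because 8.2.1 literally makes every line change an AESI.
- SAP 2.5.4 already tabulates worsening, eye-movement and visual-field results, and lists subjects with any change in visual function. SAP 2.5.2 summarizes adverse events by preferred term, so reported eye pain and visual loss can be seen. This stands: there is no basis for saying that a true signal would be buried. What the tables do not show is which events make up the AESI count.
- Diary data are kept apart, so a diary entry for pain does not by itself enter the AESI row. This stands, but pain taken from the diary as an adverse event has no classification rule.
- The illustrated size rests on an assumed rate. The tests share a baseline and a subject, so independence probably overstates it. This stands, and is why the range starts at full correlation.

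A reader might also infer that the AESI rate is the main visual-safety result. No section says so. The safety endpoints are adverse events and diary events, the safety analysis is descriptive, and the stopping rule in Protocol 8.5.8 depends on specified vascular embolic events.

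**Conclusion.** The concern holds as a defect of definition and display. The AESI wording allows line changes in either direction, the SAP's Snellen table does not, and the only AESI outputs are two undivided rows. Eye-area pain can fall under two headings with no rule between them. Scheduled retesting before month 12 is confined to injected subjects, so any retest-driven events would load onto the treated arm.

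It would be tempting to conclude that the row does not measure visual harm. The documents do not support that: it includes loss of vision, blurred and double vision, field defects and trouble moving the eyes. It is non-specific rather than uninformative.

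The size is unknown. The 2-19% range for acuity gains after initial treatment depends on an assumed 2-5% per eye-test and on within-subject correlation, and it ignores Investigator review. The primary effectiveness analysis is unaffected.

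**What to change.** In SAP 2.5.2, keep the full Any AESI count and add component rows beneath it:

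1. Snellen worsening of one line or more, by the same rule as SAP 2.5.4.
2. Snellen improvement only.
3. Other visual disturbance.
4. Pain in or around the eye, as its own row, with no event reclassified or removed. Taking out injection-site pain by medical judgement would add subjectivity and could discard real events.

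A footnote should say that, before month 12, scheduled post-baseline vision tests exist only for injected subjects.

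Protocol 8.1.1, 8.2.1 and 8.3 must be reconciled on how a line change and periorbital pain are classified. The expedited-reporting trigger need not change for this.

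The cost is a few extra table rows and the coding of AESI components before database lock. No new data are needed.
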